11.3. Subgroup Analyses

Subgroup analyses will be performed to determine the consistency of treatment effect across various demographics and baseline characteristics. Between-group treatment effect, along with its nominal 95% CI, for the primary endpoint will be estimated within each category for the following subgroups:

- Age (<65 years, ≥65 years)
- Gender (Male, Female)
- Race (White, Non-white)
- Anatomic region of resected tumor (HN, Non-HN)
- Tumor stage (II, III/IV)
- ECOG status (0, 1)

As regards the DFS endpoint, a descriptive comparison will be performed between subgroups of patients who receive adjuvant cemiplimab versus adjuvant radiation therapy versus observation after surgery.

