5.2. Efficacy Variables

5.2.1. Disease Response and Disease Recurrence

Disease response will be assessed by surgical pathology using pCR and mPR. Pathologic complete response (pCR) is defined as absence of viable cancer cells in the surgical pathology sample. Major pathologic response (mPR) is defined as $\leq 10\%$ viable cancer cells in the surgical pathology sample, in patients who have not achieved pCR. Procedures to assess pCR and mPR in the surgical pathology sample after neoadjuvant therapy are not described in this protocol but will be described in a separate charter.

Objective response rate (ORR) will be assessed by the investigator using RECIST 1.1 (Eisenhauer, 2009)(Appendix 4). Procedures for assessing ORR are outlined in Section 9.2.2.3. Confirmation of complete or partial response is not required.

Event free survival (EFS) is defined as time from first dose of neoadjuvant cemiplimab to any of the following events: progression of disease that precludes surgery, inability to undergo complete resection (R0 or R1), disease recurrence (local, regional, or distant) for patients who undergo complete resection (R0 or R1), or death due to any cause.

Disease free survival (DFS) is defined as time from surgery to first recurrence (local, regional, or distant) or death due to any cause, for patients who are free of disease (R0 or R1 resection) at completion of surgery. Patterns of failure in patients with local, regional, or distant disease recurrence will be assessed by descriptive analysis according to the procedures outlined in Section 9.2.2.5 and Section 9.2.2.6.

Overall survival (OS) will be measured as time from first dose of neoadjuvant cemiplimab to death due to any cause.

5.2.2. Changes in Planned Surgery and Post-Surgical Management (Per Investigator and Per Independent Review)

Electronic case report forms (eCRFs) will capture what the management plan would be for surgery and post-surgical management if the patient were not enrolled in a clinical trial, as well as the actual surgery that was performed and the actual post-surgical management.

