- Patients who receive adjuvant radiation therapy or enter observation only during Part 2 of the study will follow a parallel imaging schedule as described in [Section 9.1.6](#).
- The window for treatment visits is ± 3 days. In the event of a missed dose, patients will not be allowed to receive the scheduled cemiplimab dose outside of this window. Any missed doses will result in a reduction in the total number of allowable doses that may be administered.

Table 2: Schedule of Events for Screening, Neoadjuvant Cemiplimab, and Surgery (Part 1 of the Study)

Study Procedure	Screening/ Baseline ¹	Cemiplimab Treatment				Surgery	EOT1 (or Early Termination) ³
		1	22±3	43±3	64±3		
Visit Days	-28 to -1					85 (75 to 100)	30 days ± 10 after surgery
Informed Consent ²	X						
Clinical Assessments							
Medical History/Oncology History	X						
Complete Physical Examination and ECOG PS	X						X
Limited Physical Examination		X	X	X	X		
Vital Signs and Weight	X	X ⁴	X ⁴	X ⁴	X ⁴		X
Height	X						
12-Lead ECG	X						X
Laboratory Tests							
Hematology ⁵	X	X	X	X	X		X
Blood Chemistry ⁵	X	X	X	X	X		X
Pregnancy Test for WOCBP ⁶	X	X	X	X	X		X
Urinalysis	X						X
HBV, HCV, HIV	X						
INR, aPTT ⁷	X					X	
TSH (with reflex T3, free T4) ⁸	X						X
Treatment							
Cemiplimab 350 mg IV Q3W		X	X	X	X		
Surgery ⁹						X	
Response Assessment							
CT/MRI ¹⁰	X			X		X	X
Digital Photography ¹⁰	X			X		X	
Tumor Biopsy ¹¹	X		X				
Treatment Management Plan Assessment ¹²	X				X		
PD/Biomarker Analysis							
PBMC Immune Monitoring Sample		X	X				
Plasma ctDNA Sample	X						X
Whole Blood Genomic DNA (mandatory)	X ¹³						
Whole Blood Genomic DNA (optional sub-study)		X ¹⁴					
Immunogenicity							
ADASample ¹⁵		X				X	X
Patient Reported Outcomes							
EORTC-QLQ-C30 ¹⁶	X					X	

Other Assessments	
Concomitant Medications	← continuous monitoring →
Adverse Events	← continuous monitoring →

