9.1.5. Visit Schedule for Patients Who Discontinue Study Drug

9.1.5.1. Visit Schedule for Patients Who Discontinue Neoadjuvant Cemiplimab

Patients who permanently discontinue from neoadjuvant study drug due to disease progression (per RECIST 1.1; [Appendix 4](#)) or toxicity will undergo surgery (if clinically appropriate) and will return for post-surgical follow-up visit (EOT1). These patients must be followed for 90 days after last dose of cemiplimab for AE identification and reporting and are ineligible to receive adjuvant cemiplimab.

Patients who discontinue neoadjuvant therapy but achieve complete resection of all macroscopic disease (R0 or R1 resection) and who do not withdraw consent from the study will subsequently be followed by imaging per the schedule in [Table 3](#) (imaging at week 15 of Part 2 (± 10 days), week 30 (± 10 days), and week 48/EOT2 followed by imaging per the schedule in [Table 4](#) (every 4 months for the first 2 years and every 6 months for the third year), or until disease recurrence, whichever occurs first. Patients who undergo R2 surgical resection (residual gross disease) will be followed for survival only.

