9.1.6. Visit Schedule for Patients Who Receive Adjuvant Radiation Therapy or Observation Only

After surgery, management options include adjuvant cemiplimab, adjuvant radiation therapy, or observation only. A patient who receives adjuvant radiation therapy will not receive adjuvant cemiplimab (neither sequentially nor concurrently) during the study.

Patients who undergo adjuvant radiation therapy or enter observation only during Part 2 of the study will be assessed by imaging only, at week 15 (± 10 days), week 30 (± 10 days), and week 48 (± 10 days) (corresponding to the equivalent EOT2 visit for patients receiving cemiplimab). Week 0 is defined as 3 weeks (± 3 days) after the EOT1 visit. Other assessments listed in [Table 3](#) are not required for a patient who receives adjuvant radiation therapy or observation only. However, biopsy should be attempted for all patients in the event of suspected recurrence or suspected SPT as described in [Section 9.2.2.7](#).

Patients who complete the week 48 evaluation visit without disease recurrence will enter follow-up, in which they undergo imaging assessments every 4 months for the first 2 years and every 6 months for the third year.

Details regarding the adjuvant therapy received by an individual patient will be reported in the eCRF (Section 12).

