4.4.2. Secondary Efficacy Variables

The secondary efficacy variables include:

- Major pathologic response (mPR) rate per independent central pathology review: mPR is defined as failure to achieve pCR but $\leq 10\%$ viable cancer cells in the surgical pathology sample.
- pCR rate and mPR rate assessed by local pathology review: pCR and mPR will be assessed by local pathology review.
- Objective response rate (ORR) prior to surgery by investigator assessment: ORR is determined by the proportion of patients with CR or PR based on investigator-assessed evaluation using RECIST 1.1 (Eisenhauer, 2009), where there is no requirement for confirmation of CR or PR. The objective response will be measured from the first dose of neoadjuvant cemiplimab to surgery or any other new anti-cancer therapy.
- Event free survival (EFS) is defined as time from first dose of neoadjuvant cemiplimab to the first of any of the following events: progression of disease that precludes surgery, inability to undergo complete resection (R0 or R1), disease recurrence (local, regional, or distant) for patients who undergo complete resection (R0 or R1), or death due to any cause.
 - Patients who do not have an EFS event without initiation of a new anti-cancer therapy will be censored at the last evaluable tumor assessment.
 - Patients who do not have an EFS event but initiate a new anti-cancer therapy, will be censored at the last evaluable tumor assessment prior to or on the date of new anti-cancer therapy.
 - Patients who do not have any evaluable post-baseline tumor assessment and do not die will be censored on the date of first study treatment.
- Disease free survival (DFS) is defined for patients who are free of disease (R0 or R1 resection) at completion of surgery as time from date of surgery until first recurrence (local, regional, or distant) or death due to any cause.
 - Patients who do not have recurrence of tumor and alive without initiation of a new anti-cancer therapy will be censored at the last evaluable tumor assessment.

- Patients who do not have recurrence of tumor and alive, but initiate a new anti-cancer therapy, will be censored at the last evaluable tumor assessment prior to or on the date of new anti-cancer therapy.
- Patients who do not have any tumor assessment after surgery and do not die will be censored on the date of surgery.

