- Overall survival (OS) is measured from the start of treatment until death due to any cause. Patients who do not die will be censored at the last date that patient is documented to be alive.

For all the above time-to-event variables, the time to event (day) is the date of event/censor - the date of first study treatment + 1.

- Change in surgical plan in the screening period versus actual surgery after neoadjuvant cemiplimab both according to investigator review and independent surgical expert review is measured by descriptive analysis. For investigator review, the overall treatment plan formulated at a multidisciplinary tumor board, description of planned/actual surgery resection, description of planned/actual reconstruction (if applicable) and planned/actual length of inpatient hospital stay after surgery will be collected.
- Change in post-surgical management plan in the screening period versus actual post-surgical management both according to investigator review and independent surgical expert review is measured by descriptive analysis. For investigator review, radiotherapy method, radiation fractionation, duration of therapy, total dose, and adjuvant chemoradiation type (if applicable) will be collected.

For independent review, variables to assess changes in planned surgery and post-surgical management will be described in a separate charter.

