5.6.2. Analysis of Secondary Efficacy Variables

The pCR rate per local pathology review, mPR rate per independent central pathology review, mPR rate per local pathology review, and ORR prior to surgery per investigator assessment will be summarized and corresponding two-sided 95% exact CIs will be calculated by Clopper-Pearson method (Clopper, 1934).

Percent residual viable tumor (%RVT) will be summarized descriptively.

Combined efficacy based on both ORR per RECIST 1.1 and pCR and mPR per pathology review may be explored.

The distribution of EFS, DFS, and OS will be estimated using the Kaplan-Meier method. The median EFS, median DFS, and median OS along with 95% CIs will be presented and Kaplan-Meier estimates with 2-sided 95% CIs at specific time points will be summarized. The Kaplan Meier curves will be presented.

As regards the DFS endpoint, a descriptive summary will be performed for each subgroup of patients who receive adjuvant cemiplimab, adjuvant radiation therapy, and observation after surgery.

Change in planned surgery will be summarized descriptively. The proportion of patients for whom the surgical management plan (at time of screening) differed from the actual surgery after neoadjuvant therapy will be summarized both by investigator assessment and independent surgical expert committee.

Change in planned post-surgical management will be summarized descriptively. The proportion of patients for whom radiation therapy (or chemoradiation) was planned during screening but not actually administered after neoadjuvant cemiplimab and surgery will be summarized.

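### The DFS summary by adjuvant option starts the clock at surgery but groups patients by treatment received weeks later, so the cemiplimab and radiation groups carry guaranteed event-free time

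*Protocol*

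**What the plan says.** **Grouping.** Protocol 11.3 says that "a descriptive comparison will be performed between subgroups of patients who receive adjuvant cemiplimab versus adjuvant radiation therapy versus observation after surgery". SAP 5.6.2 changes the noun but not the groups: "a descriptive summary will be performed for each subgroup of patients who receive adjuvant cemiplimab, adjuvant radiation therapy, and observation after surgery". SAP 1.2.4 removes the other subgroup efficacy analyses; this one stays.

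**Time origin.** Protocol 5.2.1 defines DFS as "time from surgery to first recurrence (local, regional, or distant) or death due to any cause", for patients with an R0 or R1 resection. SAP 4.4.2 agrees: "time from date of surgery until first recurrence (local, regional, or distant) or death due to any cause". The same SAP section then gives one day count for all the time-to-event variables, in which "the time to event (day) is the date of event/censor - the date of first study treatment + 1". That conflicts with its own DFS origin.

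**When adjuvant treatment starts.** Protocol Table 2 (Section 9.1) places EOT1 at "30 days ± 10 after surgery". For radiation and observation patients, Protocol 9.1.6 says "Week 0 is defined as 3 weeks" (± 3 days) after EOT1; Section 9.1 gives the same definition and starts adjuvant cemiplimab then. Footnote 2 to Table 3 moves a missed first dose to week 3.

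**Who can enter the cemiplimab group.** Recurrence in the adjuvant portion permanently stops study drug (Protocol 8.3.1). Patients who stopped neoadjuvant drug for progression or toxicity "are ineligible to receive adjuvant cemiplimab" (Protocol 9.1.5.1). Otherwise the option is at the patient's and investigator's discretion (Protocol 6.1.3).

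Neither document gives a landmark, a time-dependent method, a separate time origin for this display, or a rule for patients with an event before any adjuvant option begins.

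**The concern.** Group membership is decided after the clock has started. A patient counted under adjuvant cemiplimab must have lived without a documented recurrence until the first dose, so that stretch of the group's DFS curve cannot contain an event. This is immortal time. The radiation group has the same feature up to its own start, which the documents do not date. Observation needs no start, so it has no comparable protected period.

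Protocol 3.2.3 and SAP 1.1 both say that Part 2 data could inform a future randomised trial of adjuvant therapy. A reader planning that trial would look at this display, and part of any advantage for the active options could come from how the groups are built.

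**Working it through.** The documents state no figure for the gap between surgery and adjuvant treatment, so there is none to reproduce. It follows from the visit windows.

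1. **On-schedule first dose.** EOT1 is 30 ± 10 days after surgery, so day 20 to 40. The first dose is 21 ± 3 days after EOT1, so 18 to 24 days later.
   - Minimum: 20 + 18 = 38 days.
   - Nominal: 30 + 21 = 51 days.
   - Maximum: 40 + 24 = 64 days.

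2. **Week 0 missed, start at week 3.** The first dose is 42 ± 3 days after EOT1: 20 + 39 = 59 to 40 + 45 = 85 days after surgery.

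3. **Chance of documenting an event in the gap.** Imaging at EOT1 is optional (footnote 10 to Table 2). The first required post-surgical scan is at week 15 ± 10 days: 38 + 105 − 10 = 133 to 64 + 105 + 10 = 179 days after surgery, on the same schedule for all three options. What can surface earlier is a death, a recurrence found clinically or on pathology, or one seen on an unscheduled or optional scan.

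4. **Literal use of the SAP day count.** With surgery on study day 75 to 100, the first adjuvant dose falls on about study day 75 + 38 = 113 to 100 + 64 = 164. The pre-surgical time is added in every group, so the gap specific to grouping is still 38 to 64 days.

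5. **Illustrative size.** The documents give neither group sizes nor an expected DFS. The assumptions here are a constant hazard with no true difference between options, 2-year DFS S of 60% to 90%, all 76 patients entering DFS (an upper bound), a fraction f of 50% to 70% heading for cemiplimab and the rest for observation, and a gap T of 38 to 64 days. Radiation is left out for simplicity.
   - Hazard h = −ln(S)/730.5; probability of an early event p = 1 − exp(−hT). This gives p from 0.55% (S = 90%, T = 38) to 4.38% (S = 60%, T = 64). In patients: 76 × 0.0055 = 0.4 to 76 × 0.0438 = 3.3.
   - Cemiplimab group's 2-year DFS = exp(−h(730.5 − T)).
   - If early events among those heading for cemiplimab are counted as observation, observation DFS = 76(1 − f)S / [76(1 − f) + 76fp].
   - Example with S = 80%, f = 50%, T = 38: p = 1.15%; patients moved 38 × 0.0115 = 0.44; cemiplimab 0.809; observation 30.4/38.44 = 0.791; gap 1.8 points.
   - Over the full range, the gap runs from 0.905 − 0.895 = 1.0 point (S = 90%, f = 50%, T = 38) to 0.627 − 0.544 = 8.3 points (S = 60%, f = 70%, T = 64).
   - If those patients are instead left out of every group, while early events among patients heading for observation still count, the gap is exp(−h(730.5 − T)) − S, or 0.49 to 2.75 points.
   - If all early events up to the same day are left out of all groups, both curves equal exp(−h(730.5 − T)) and the gap is zero. That is what a landmark does.

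**The case against.** A reader might infer that anyone who recurs or dies before week 0 becomes an observation patient, so that early events can fall only outside the cemiplimab group. The documents do not say this. Observation is a Part 2 option, every patient must give separate Part 2 consent whichever option follows (Protocol 6.1.7), and recurrence leads to survival follow-up (Protocol 9.1.7). A patient with an early event may belong to none of the three groups. If membership of every group required consent at EOT1, the first 20 to 40 days would be protected for all, and the part specific to cemiplimab would be about 18 to 24 days. This stands: the 1 to 8 point figure depends on a classification that the plan leaves open.

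It is also fair that radiation patients have guaranteed time of their own, that few recurrences will be documented before the first required scan, and that the SAP promises a descriptive summary with no test and no explicit set of curves by option. Both documents add that the primary objective concerns neoadjuvant, not adjuvant, treatment. These points limit the size and the consequences. They do not remove the guaranteed time, because deaths and clinically evident recurrences count. EOT1 also includes a complete physical examination and is the visit where Part 2 consent is normally sought, so a recurrence found there changes the patient's path.

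Finally, choice of option by prognosis may outweigh a few weeks of guaranteed time and could act in any direction. A landmark does not remove that. It does remove a separate, avoidable bias.

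**Conclusion.** The concern holds as a defect in one descriptive secondary display. As written, the adjuvant cemiplimab group carries 38 to 64 days of time free of documented events when dosing is on schedule, and up to about 85 days for week 3 starters. Radiation carries an unspecified amount, and observation none comparable. The plan is also silent on where patients with earlier events go.

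The effect is probably modest. Under the stated assumptions, about 0 to 3 patients have an event in the gap. The spurious 2-year difference is about 1 to 8 points if those heading for cemiplimab are counted as observation, and 0.5 to 2.75 points if they are placed in no group. Both ranges treat events as documented when they occur, so sparse early imaging would tend to lower them.

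Two stronger conclusions are not supported: that early events are assigned to observation by rule, and that the net difference between options must favour cemiplimab. Investigator choice and the eligibility bar also shape the groups. The primary pCR analysis and overall DFS from surgery are unaffected.

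**What to change.** For the DFS display by adjuvant option only, amend SAP 5.6.2 to use a landmark:

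- **Origin.** Either Part 2 week 0, already defined for all three options, or a fixed day after surgery late enough to cover week 3 starters, about day 85. With week 0, grouping by treatment already started would put week 3 starters under observation unless a recorded plan is used; the fixed day avoids this.
- **Who is included.** Patients alive, free of documented recurrence and in follow-up at the landmark.
- **Grouping.** By the option started on or before the landmark, from recorded dosing and radiation dates; patients who had started neither count as observation. The plan at week 0 could be used instead if it is captured, but Protocol 5.2.2.2 lists no such field. Patients starting an option later stay in their landmark group.
- **Exclusions.** Report the number excluded for earlier events, by option where one had begun and as a single total where none had.
- **Caveat beside the display.** The option was chosen by the investigator, and patients who stopped neoadjuvant drug for progression or toxicity could not receive adjuvant cemiplimab, so selection remains.

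Keep overall DFS from surgery, and correct the SAP 4.4.2 day count so that DFS is counted from the surgery date. The cost is SAP wording and a simple re-derivation from recorded dates, with no new patient procedures. The downside is that a few early events drop out of this display; they remain in overall DFS.

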11.4. Analysis Sets

11.4.1. Efficacy Analysis Sets

The full analysis set (FAS) will include all enrolled patients. Efficacy endpoints will be analyzed using the FAS.

11.4.2. Safety Analysis Set

The safety analysis set (SAF) will include all enrolled patients who received at least one dose of cemiplimab. Treatment compliance/administration and all clinical safety variables will be analyzed using the SAF.

11.4.3. PK Analysis set

The PK analysis set includes all patients who received at least 1 dose of cemiplimab (SAF) and who had at least 1 non-missing cemiplimab concentration following the first dose of cemiplimab.

11.4.4. Immunogenicity Analysis Sets

The ADA analysis set includes all subjects/patients who received study drug and had at least 1 non-missing ADA result following the first study dose.

The neutralizing antibody (Nab) analysis set includes all patients who received any study drug and who are negative in the ADA assay or with at least 1 non-missing result in the NAb assay (patients who are ADA negative are set to negative in the NAb analysis set).

11.4.5. Exploratory Pharmacodynamic and Biomarker Analysis Set

The biomarker analysis set for each analysis includes all patients who received cemiplimab and who have data available from baseline.

11.5. Statistical Methods

For continuous variables, descriptive statistics will include the following information: the number of patients reflected in the calculation (n), mean, standard deviation, Q1, median, Q3, minimum, and maximum.

For categorical or ordinal data, frequencies and percentages will be displayed for each category.

